#### 11.5 General Statistical Analysis Considerations

The primary efficacy analysis will include only Part 2 data. Due to the early stopping of Part 1 enrollment, for secondary and exploratory efficacy endpoints, the efficacy data from the SABER®-Bupivacaine arm from Part 1 will be integrated with the same treatment arm from Part 2 and be compared to bupivacaine HCl (75 mg) over 72 hours. Inferential statistics will be derived from the comparison. Due to lack of full enrollment of subjects from Part 1, the efficacy will be descriptive, presented as either mean or ratio and its 95% confidence interval as appropriately applied.

Continuous variables will be generally summarized using descriptive statistics such as mean, median, standard deviation, standard error and ranges. Categorical variables will be summarized using frequencies and percentages. 95% confidence intervals will also be provided when appropriate. Inferential tests for the analysis of continuous variables will be primarily based on parametric general linear models and will be 2-sided and conducted at the overall 5% significance level unless otherwise stated.

The multiplicity of comparisons impact on the Type 1 error rate will be addressed below ([Section 11.8.4](#)). In the case where the general linear model assumptions appear to be significantly violated, nonparametric methods of analysis such as the Wilcoxon Rank-Sum test will be used. A data transformation will also be made in an attempt to achieve a successful normalization of non-normal data. Inferential tests for categorical variables will be based on logistic regression models and categorical data analysis models. In cases where the cell counts (i.e. percentages) are too small for asymptotic methods to be valid, exact tests such as Fisher's exact test will be used.

Unless otherwise specified, all statistical tests will be conducted employing a two-sided significance level of 0.05.

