### 11.3 Patient Randomization

#### Part 1

It was planned that approximately 320 eligible patients would be randomized, in order to obtain 306 evaluable patients (i.e., patients who received any test drug and have at least one post-surgical pain intensity score). It had been estimated that 5% of randomized patients may not receive any test drug due to unforeseeable intra-operative exclusion. Patients would be randomized in a 1:1 ratio to receive one of two treatments based on a computer-generated randomization schedule prepared before the study:

- Treatment Group 1: SABER®-Bupivacaine 5 mL (132 mg/mL, 660 mg bupivacaine base)
- Treatment Group 2: Sterile normal saline 5 mL (0.9% sodium chloride injection, USP) (placebo)

Due to the early administrative stopping, only approximately 90 subjects will be enrolled and randomized in Part 1.

#### Part 2

Approximately 274 eligible patients will be randomized, in order to obtain 264 evaluable patients (i.e., patients who are randomized and received any test drug). It has been estimated that 4% of randomized patients may not receive any test drug due to unforeseeable intra-operative exclusion. Patients will be randomized in a 1:1 ratio to receive one of two treatments based on a computer-generated randomization schedule prepared before the study:

- Treatment Group 3: SABER®-Bupivacaine 5 mL (132 mg/mL, 660 mg bupivacaine base)
- Treatment Group 4: Bupivacaine HCl without epinephrine, 15 mL of 0.5% solution (75 mg)

For both Part 1 and 2, the randomization will be balanced by using randomly permuted blocks (block size of 4) and will be stratified by sex. The rationale for stratification by sex was differences in pain response reported in the literature for both acute/chronic pain ([Fillingim et al, 2009](#)), postoperative pain studies in cholecystectomy ([De Cosmo et al, 2008](#); [Uchiyama et al, 2006](#)) and a previous laparoscopic cholecystectomy trial (C803-025, Cohort 2) conducted by DURECT. [De Cosmo et al](#) found that females had a higher mean pain score ( $4.3 \pm 2.1$ ) than males ( $2.9 \pm 1.6$ ) during 24 hours postoperatively ( $p=0.003$  from repeated measure ANOVA). A significant sex effect on 24-hour postoperative pain was also reported by [Uchiyama et al](#).

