##### *Alternate hypothesis:*

There is a difference in analgesic effect between subjects treated with SABER®-Bupivacaine and those treated with bupivacaine HCl, as measured by pain intensity on movement scores over 0-48 hours following test drug administration, with adjustment for sex effect and imputation for missing pain scores.

The pain scores will be analyzed by a mixed effect ANOVA model of repeated measures (MMRM). The model includes the following fixed effects: sex stratum, treatment, sex by

treatment, time, interaction of treatment and time, study site and interaction of study site and treatment, with time as the repeating factor and subject as a random effect.

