#### 11.8.2 Secondary Efficacy Endpoints

For all secondary efficacy endpoints, data from SABER®-Bupivacaine arm in Part 1 will be combined with the same treatment arm in Part 2. The integrated data will be compared to Bupivacaine HCl.

The key secondary efficacy endpoint:

- Pain intensity on movement measured at scheduled time points from 0-72 hours following test drug administration, adjusted for prior rescue medication use and analyzed by a mixed effect ANOVA model of repeated measures (MMRM).

The adjustment algorithm for rescue medication use is the same as described for the primary endpoint in [Section 11.8.1](#).

Additional secondary efficacy endpoints:

- Total IV morphine-equivalent dose of rescue opioids used during 0-72 hours following test drug administration (standard conversion factors will be used to convert different opioids to IV morphine-equivalents; CCI)

- Composite endpoint of Silverman's Integrated Analgesic (SIA) assessment score (Dai et al, 2013 and Silverman et al, 1993) over 0-72 hours following test drug administration
- Proportion of patients taking no opioid rescue medication from PACU discharge until 72 hours after test drug administration
- Time to first opioid rescue medication use after discharge from the PACU
- Time to PACU discharge eligibility as assessed by mPADSS (Chung, 1995; Awad and Chung, 2006).

The total IV morphine-equivalent dose of opioid rescue medication used during the first 72 hours post-dose will be analyzed by an ANOVA model adjusted for the stratification or by the van Elteren test (a stratified Wilcoxon Rank Sum test), depending on whether normality assumptions have been met.

A composite endpoint, Score of Integrated Analgesia (SIA) (Dai et al, 2013 and Silverman et al, 1993), that integrates pain assessment score with opioid use will be derived at 24, 48 and 72 hours post-surgery. The score derived for each subject represents a sum of the ranks (ranging from -200 to 200 with -200 being the best case and 200 the worst case). SIA will be analyzed by repeated measures ANOVA. The model will have treatment, sex, sex\*treatment interaction and study site as the main effects, subject as the random effect and time as the repeating factor.

[figure not shown]
The categorical efficacy endpoint, proportion of patients taking no opioid rescue medication will be compared between the two treatment groups using the Cochran-Mantel-Haenszel (CMH) test stratified by sex.

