Time to the first use of rescue opioid after discharge from PACU will be analyzed using the Kaplan-Meier method. Subjects who do not use any rescue opioids will be censored at 72 hours. The stratified Log rank test will be used to compare the treatment groups.

Time to PACU discharge eligibility by mPADSS will be analyzed by Kaplan-Meier method and compared between the treatment groups by stratified Log rank test.

CCI

CCI

CCI

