#### 11.8.4 Adjustment for Multiple Hypotheses Testing

The serial gate-keeping approach (proposed by [Westfall and Krishen, 2001](#)) will be used to test the primary and secondary endpoints (order by its clinical relevance and importance) in the above specified sequence. It will be implemented in the following way: If (and only if) the null hypothesis associated with primary endpoint has been rejected at the 0.05 level, then the first secondary endpoint, movement pain adjusted for rescue medication use during the first 72 hours following administration of test drug will then be tested. If this second gate-keeping step has been passed, the next secondary endpoint will be tested until the p-value > 0.05, then no more formal hypothesis testing will be performed. Once this occurs, the additional endpoints will be analyzed in order to engender additional hypotheses concerning their effects.

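### The gatekept secondary tests add about 45 Part 1 SABER-Bupivacaine patients, never randomised against bupivacaine HCl, to one side of the comparison, with no Part term in any described model

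*Combined protocol and SAP*

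**What the plan says.** - **Primary.** Sections 11.4, 11.5 and 11.8 restrict the primary efficacy analysis to Part 2.
- **Secondaries.** Section 11.5 says that the Part 1 SABER-Bupivacaine data "will be integrated with the same treatment arm from Part 2 and be compared to bupivacaine HCl (75 mg) over 72 hours" and that the comparison yields inferential statistics. Section 11.8.2 applies this to all secondary endpoints: "The integrated data will be compared to Bupivacaine HCl".
- **Testing.** Section 11.8.4 starts with the primary and moves to 0–72 h pain if the primary is significant. It then continues: "If this second gate-keeping step has been passed, the next secondary endpoint will be tested until the p-value > 0.05".
- **Arms.** Sections 5.4.1 and 11.3 give saline as the only Part 1 comparator; bupivacaine HCl appears only in Part 2. Randomisation uses "randomly permuted blocks (block size of 4) and will be stratified by sex".
- **Models.** The MMRM in section 11.8.1 includes "interaction of treatment and time, study site and interaction of study site and treatment". In section 11.8.2 the SIA model names study site. Total opioid dose is adjusted for the stratification or analysed by the van Elteren test. The opioid-free proportion uses the "Cochran-Mantel-Haenszel (CMH) test stratified by sex". For time to first opioid, "The stratified Log rank test will be used to compare the treatment groups", and time to PACU discharge eligibility is handled the same way. No analysis includes Part or enrolment period.
- **An unclear sentence.** Shortly after calling the comparison inferential, section 11.5 says "Due to lack of full enrollment of subjects from Part 1, the efficacy will be descriptive". This probably means Part 1's own comparison with saline, but the text does not say so.

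**The concern.** Randomisation protects the Part 2 contrast only. Once Part 1 SABER patients are added to one side, any difference between the Parts that the model does not absorb enters the SABER–HCl estimate.

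The documents give reasons why the Parts could differ:

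- A Part 1 patient could receive saline, while every Part 2 patient receives an active drug. Expectation could affect self-reported pain and requests for rescue.
- Part 1 enrolment ends according to when sites are ready for Part 2 (section 11.2), so site mix and calendar time may differ.
- The protocol was amended during enrolment (note in section 7.4.10).

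The gate does not remove the problem. If all null hypotheses are true, the Part 2-only primary keeps the overall error at 5%. The exposure arises when the primary succeeds and a later null is true. That is unlikely for 0–72 h pain, which contains the 0–48 h scores. It is more plausible for opioid use and the time-to-event endpoints, which are the four analyses with no named site term. A difference favouring SABER raises the rate of false claims; one against SABER costs power.

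**Working it through.** **Inputs from the documents.** Part 1 enrols about 90 patients, 1:1, so 90/2 = 45 on SABER. Part 2 has 132 evaluable per arm, 90% power and two-sided alpha 0.05. The effect size is redacted.

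**Plan's own figures.** 264/(1 − 0.04) = 275, against 274 stated, so this reproduces within rounding. The effect that gives 90% power with 132 per arm is (1.960 + 1.282) × √(2/132) = 3.242 × 0.1231 = 0.399 SD. I use 0.40 SD, which gives 90.1% power.

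**Pooled comparison.**
- SABER arm: 132 + 45 = 177. Share never randomised against HCl: 45/177 = 25.4%.
- SE pooled = √(1/177 + 1/132) = 0.1150 SD. SE Part 2 only = √(2/132) = 0.1231 SD. Ratio 1.070.
- Bias from a Part difference of d SD = 0.254d.

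**Error rates.** The value of d is not in the documents; I assume 0 to 0.5 SD, with no site adjustment. With b = 0.254d/0.1150, the stand-alone two-sided error is Φ(−1.96 + b) + Φ(−1.96 − b).

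The gated error is the bivariate normal probability that both the primary and the secondary exceed 1.96 in absolute value. The primary has mean 0.40/0.1231 and the secondary has mean b. The correlation is ρ × 0.934 with ρ = 0, 0.3 or 0.5, where 0.934 = 0.1150/0.1231. The column gives the range over ρ for a difference favouring SABER.

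| d (SD) | Stand-alone error | Gated error, primary effect 0.40 SD |
|---|---|---|
| 0 | 5.0% | 4.0–4.5% |
| 0.1 | 5.6% | 4.9–5.1% |
| 0.2 | 7.3% | 6.6–6.8% |
| 0.3 | 10.2% | 9.2–9.9% |
| 0.5 | 19.7% | 17.8–19.4% |

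Total opioid dose is the third endpoint tested. With the key secondary effect also at 0.40 SD, simulation of 2,000,000 trials (primary–key secondary correlation 0.9, opioid correlation 0 to 0.5) gives 3.8–4.4% at d = 0, 9.2–9.8% at 0.3 and 17.8–19.4% at 0.5.

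**Sensitivity to the Part 1 count.** With 40, 43 or 50 Part 1 SABER patients, stand-alone error at 0.3 SD is 9.3%, 9.8% or 11.1%.

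**Does a site term help?** Two simulations of 4,000 trials each, with 15 assumed sites, tested a calendar difference with site main effects in the model:

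| Assumed source of Part 1 patients | d = 0.3, without / with site | d = 0.5, without / with site |
|---|---|---|
| 7 of the 15 sites | 10.0% / 8.6% | 18.6% / 14.5% |
| All 15 sites | 9.8% / 10.1% | 17.2% / 17.6% |

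Site adjustment removes little or none of it.

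**Does a Part term help?** Part 1 has no HCl patients, so with a Part term the treatment contrast comes from Part 2 alone. In a simulated data set the estimate with a Part term equalled the Part 2-only difference, 0.0464 in both. The bias goes, and so does the gain from pooling.

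**What pooling buys.** Power at 0.40 SD rises from 90.1% to 93.6% if d = 0. Adverse drift of 0.40 × (1 − 0.1150/0.1231)/0.254 = 0.103 SD cancels this. At 0.3 SD against SABER, pooled power is Φ((0.40 − 0.0763)/0.1150 − 1.96) = 80.4%.

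**The case against.** The strongest counter-argument is that the harm rests on an input found nowhere in the documents. Both Parts share eligibility, anaesthesia, surgical, rescue and pain-assessment rules, and the same SABER dose and technique. Part 1 data stay blinded until Part 2 ends. At d = 0.1 SD the gated error is about nominal. Pooling also has the lower mean squared error until 0.254d exceeds √(0.1231² − 0.1150²) = 0.044 SD, that is, below about 0.17 SD. The pooling is openly prespecified, and a Part 2-only sensitivity analysis would be a lighter remedy.

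It is fair that the size is hypothetical and that a small difference would do little damage. That does not justify non-randomised patients in a confirmatory test, where the requirement is control of false claims and the difference has no documented bound. A sensitivity analysis would leave the formal claim on the unprotected comparison.

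Several narrower points stand as qualifications:

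- Section 11.2 can be read as a site-by-site switch, so enrolment in the Parts may overlap. The Part 1 patients would still not have been randomised against HCl.
- The log rank strata are not named. Sex is inferred because it is the only randomisation stratifier.
- The site term for 0–72 h pain is inferred from the primary MMRM; section 11.8.2 restates only the rescue adjustment.
- Section 11.8.6 mentions pooled small sites in secondary analyses, yet four of the methods name no site term.
- The error figures are on a normal scale; nothing was computed specifically for the CMH or log rank tests.
- Some text is redacted, and section 11.6 refers to a separate SAP. The absence of a Part term is therefore a statement about the methods visible here. The pooling rule itself is fixed in sections 11.5 and 11.8.2.

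**Conclusion.** The concern holds and should be fixed. The plan tests its secondary hypotheses on a SABER arm of which about a quarter was not randomised against the comparator, and no described model separates the Parts. The missing Part term matters more than the missing site terms.

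The bias formula and standard errors follow from the planned numbers. The error rates are conditional on an assumed Part difference, the back-solved 0.40 SD effect and a successful primary. On those assumptions, false rejection of a null secondary stays near nominal at 0.1 SD, roughly doubles at 0.3 SD and approaches 20% at 0.5 SD. Direction is unknown, so the effect could instead be lost power. The primary result is not touched.

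**What to change.** - **Sections 11.5 and 11.8.2:** run the key secondary and all other gatekept secondary tests in the Part 2 mITT set, as for the primary, and make section 11.4 match.
- **Pooled comparison:** keep it as a labelled supportive analysis outside the sequence in section 11.8.4.
- **Section 11.5:** reword the inferential and descriptive sentences so that each names the comparison it covers.

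A Part term is not a substitute if the aim is to keep the precision gain.

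The cost is protocol and SAP wording, which can be settled before unblinding, and no extra patients. Standard errors on the secondary endpoints widen by about 7%, and power at 0.40 SD is 90.1% instead of 93.6% if the Parts do not in fact differ.

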## 11.6 Methodology for Dropouts and/or Missing Data

### Imputation for Missing Pain Score

For the primary efficacy endpoint (scheduled pain on movement, adjusted for prior rescue medication use) the repeated measures ANOVA will handle data missing at random. However, detailed tabulation of the amount, percentage of subjects, and pattern of missing data by treatment group over time will be presented. Two approaches will be used to impute a missing pain score. For any dropout prior to 72 hours due to adverse event or lack of efficacy, a single imputation of worst value carried forward (WOCF; [FDA, 2014](#)) will be used. For dropouts due to other reasons or intermittent missing values, a multiple imputation algorithm (Markov Chain Monte Carlo method [MCMC]) will be used ([Yuan, 2010](#)). The detailed implementation of these analyses will be described in a separate Statistical Analysis Plan (SAP).

### Rescue Medication Use

If it is indicated on the LogPad that no rescue medication was used, a dose of zero milligrams will be imputed. The lack of rescue medication use will be verified using data from the site rescue medication reconciliation/pill count. If there is a discrepancy between the rescue medication entered in the LogPad and the pill count at the study visit, the LogPad results will be used for analysis.

### Time-to-Event Variables

For any time to event variable (e.g., time to the first use of a rescue opioid after discharge from the PACU), the Kaplan-Meier method will be used to analyze it by using the event time when a subject has the first event or the entire follow-up time when a subject does not have the event. For the latter, the variable will be censored at the time of last follow-up. No imputation will be made.

## 11.7 Demographic and Baseline Characteristics

For Part 1 and 2, continuous variables will be summarized using descriptive statistics such as mean, median, standard deviation, standard error and ranges. Categorical variables will be

summarized using frequencies and percentages. 95% confidence intervals will also be provided when appropriate.

### 11.8 Statistical Analyses of Efficacy Endpoints

The principal analyses of the primary efficacy endpoint will be carried out based on the modified Intention-to-Treat (mITT) set comprising all randomized patients who receive trial drug in Part 2.

#### 11.8.1 Primary Efficacy Endpoint

##### Part 2

The primary efficacy endpoint is:

- Pain intensity on movement measured at scheduled time points from 0-48 hours following test drug administration, adjusted for prior rescue medication use and analyzed by a mixed effect ANOVA model of repeated measures (MMRM)

To account for the impact of rescue medication use on the scheduled pain scores, the following substitution method will be used. If the scheduled pain on movement score has been assessed within one plasma half-life after the use of rescue medication (IV or oral opioid, or acetaminophen), and if the pre-rescue medication pain score is higher than the scheduled one, the pain score will be censored and the rescue medication pain score will substitute for it (FDA, 2014). If any of the rescue pain scores are missing, then the worst pain score up to that point will be used instead.

Data derived from the assessment of pain intensity on movement will be used to test the hypotheses as described below:

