#### 5.4.2 Primary and Secondary Endpoints

The primary efficacy endpoint is:

- Pain intensity on movement measured at scheduled time points from 0-48 hours following test drug administration, adjusted for prior rescue medication use and analyzed by a mixed effect ANOVA model of repeated measures (MMRM).

To account for the impact of rescue medication use on the scheduled pain scores, the half-life substitution method will be used. Specifically, if the scheduled pain score has been assessed within one plasma half-life after the use of rescue medication (IV or oral opioid or oral acetaminophen), and if the pre-rescue medication pain score is higher than the scheduled one, then the pain score recorded at the time of rescue medication administration will be substituted for the scheduled pain score (FDA, 2014). If a rescue medication pain score is missing, then the worst pain score up to that point will be substituted instead.

The key secondary efficacy endpoint is:

Pain intensity on movement measured at scheduled time points from 0-72 hours following test drug administration, adjusted for prior rescue medication use and analyzed by a mixed effect ANOVA model of repeated measures (MMRM). Additional secondary endpoints are:

- Total IV morphine-equivalent dose of rescue opioids used during 0-72 hours following test drug administration (standard conversion factors are used to convert different opioids to IV morphine-equivalents; CCI [REDACTED])
- Composite endpoint of Silverman's Integrated Analgesic (SIA) assessment score (Dai et al, 2013 and Silverman et al, 1993) over 0-72 hours following test drug administration
- Proportion of patients taking no opioid rescue medication from PACU discharge until 72 hours after test drug administration
- Time to first opioid rescue medication use after discharge from PACU
- Time to PACU discharge eligibility as assessed by mPADSS (Chung, 1995; Awad and Chung, 2006)

CCI

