## 8.0 Assessment of Efficacy

### 8.1 Efficacy Assessments

#### Primary Efficacy Endpoint:

- Pain intensity on movement measured at scheduled time points from 0-48 hours following test drug administration, adjusted for prior rescue medication use and analyzed by a mixed effect ANOVA model of repeated measures (MMRM).

To account for the impact of rescue medication use on the scheduled pain scores, the half-life substitution method will be used. Specifically, if the scheduled pain score has been assessed within one plasma half-life after the use of rescue medication (IV or oral opioid or oral acetaminophen), and if the pre-rescue medication pain score is higher than the scheduled one, then the pain score recorded at the time of rescue medication administration will be substituted for the scheduled pain score (FDA, 2014). If a rescue medication pain score is missing, then the worst pain score up to that point will be substituted instead

Key Secondary Efficacy Endpoint:

Pain intensity on movement measured at scheduled time points from 0-72 hours following test drug administration, adjusted for prior rescue medication use and analyzed by a mixed effect ANOVA model of repeated measures (MMRM). Additional Secondary Efficacy Endpoints:

Total IV morphine-equivalent dose of rescue opioids used during 0-72 hours following test drug administration (standard conversion factors are used to convert different opioids to IV morphine-equivalents; CCI [REDACTED])

- Composite endpoint of Silverman’s Integrated Analgesic (SIA) assessment score (Dai et al, 2013 and Silverman et al, 1993) over 0-72 hours following test drug administration
- Proportion of patients taking no opioid rescue medication from PACU discharge until 72 hours after test drug administration
- Time to first opioid rescue medication use after PACU discharge
- Time to PACU discharge eligibility as assessed by mPADSS (Chung, 1995; Awad and Chung, 2006)

CCI [REDACTED]

[REDACTED]

[REDACTED]

[REDACTED]

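### The rescue substitution covers only scheduled pain scores that were recorded; when one is missed soon after rescue, no stated rule uses the recorded pre-rescue score

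*Combined protocol and SAP*

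**What the plan says.** The rule for the primary endpoint in Section 11.8.1 has two conditions. The first is "If the scheduled pain on movement score has been assessed within one plasma half-life after the use of rescue medication". The second is that "if the pre-rescue medication pain score is higher than the scheduled one, the pain score will be censored and the rescue medication pain score will" take its place. Section 5.4.2 has the same trigger ("if the scheduled pain score has been assessed within one plasma half-life after the use of rescue medication"), and Section 8.1 repeats the comparison with the scheduled score ("if the pre-rescue medication pain score is higher than the scheduled one, then the pain score recorded at the time of rescue medication administration will" replace it). Section 11.8.2 carries the algorithm over to the key secondary endpoint at 72 hours.

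The rule has one clause on missing data, and it concerns the rescue score, not the scheduled score: "If any of the rescue pain scores are missing, then the worst pain score up to that point will be used instead".

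Section 11.6 deals with missing scheduled scores. "For any dropout prior to 72 hours due to adverse event or lack of efficacy, a single imputation of worst value carried forward" applies; otherwise, "For dropouts due to other reasons or intermittent missing values, a multiple imputation algorithm (Markov Chain Monte Carlo method [MCMC]) will be used". It does not mention rescue use or pre-rescue scores. It leaves the detailed implementation to a separate SAP, whose text is not in the document reviewed here.

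Sections 5.7.2 and 7.5 require a pain-on-movement score before each oral rescue dose and keep it on the diary through Study Day 4. The score therefore exists independently of the scheduled entry.

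**The concern.** The substitution exists because a score taken soon after rescue understates the pain that led to the rescue. A missed entry in the same window poses the same problem, yet it meets neither condition: nothing was assessed, and there is no scheduled value to compare. It then becomes an ordinary intermittent gap, filled from a model in which pre-rescue scores have no stated place.

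The plan is cautious when the pre-rescue score is missing, since it takes the worst score so far. It is silent when the scheduled score is missing and a high pre-rescue score is on file. Such gaps are foreseeable. Scheduled scores fall at 1, 4, 6, 8 and 10 hours on the day of surgery (Section 7.4.2.1), rescue doses can fall shortly before them, and Section 9.2.1.2 lists somnolence among the solicited events, many of which it links to opioids. At stake are the adjusted pain scores behind the primary and key secondary endpoints.

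**Working it through.** **1. The stated rules side by side, for a scheduled time within one half-life after rescue**

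| Scheduled score | Situation | Value analysed |
|---|---|---|
| Recorded | Pre-rescue score recorded and higher | Pre-rescue score |
| Recorded | Pre-rescue score missing | Worst score so far |
| Missed | Patient continues | MCMC imputation; pre-rescue score not mentioned |
| Missing | Dropout for adverse event or lack of efficacy | WOCF; not stated whether pre-rescue scores count |

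The third row is the gap. The order of substitution and imputation, and the variables in the imputation model, are not stated.

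**2. One patient (invented scores)**

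Pre-rescue score 9 at 5.5 h, 4 h score 5, 6 h entry missed, 8 h score 3. Assume substitution comes before imputation, and use the midpoint of the neighbouring scores as a rough stand-in for the imputed mean. The 8 h score is 8 − 5.5 = 2.5 h after rescue. No half-life is visible in the text, so both cases are shown.

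- Half-life from 0.5 h to under 2.5 h: the 8 h score stays 3, and the imputed 6 h value is near (5 + 3)/2 = 4.
- Half-life of 2.5 h or more: the 8 h score itself becomes 9, and the imputed 6 h value is near (5 + 9)/2 = 7.

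Had the patient entered 3 at 6 h, the analysed value would be 9. The shortfall is 9 − 4 = 5 or 9 − 7 = 2.

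**3. Size at the affected points (simulation, assumed inputs)**

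One time point with 0-10 scores, within-patient correlation about 0.5, rescue taken at a pre-rescue score of 6 or more, and missed entries imputed from the neighbouring scheduled scores.

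| Share of scores affected | Rule's value | Imputed value | Gap | Fall in arm mean |
|---|---|---|---|---|
| 6.1% | 7.20 | 6.22 | 0.98 | 0.061 × 0.98 = 0.06 |
| 18.2% | 7.19 | 6.10 | 1.09 | 0.182 × 1.09 = 0.20 |

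**4. Effect on the treatment difference (assumed inputs)**

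The plan gives no figure on this point to reproduce, and the Part 2 effect size is redacted. For 132 per arm, 90% power and two-sided 5%, the implied standardised effect is (1.960 + 1.282) × √(2/132) = 0.399, so 0.40 is used. The SDs of 1.6 and 2.1 are those quoted for men and women from a cited study in Section 11.3. This gives differences of 0.40 × 1.6 = 0.64 and 0.40 × 2.1 = 0.84.

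If m is the share of scores missed after rescue in each arm and g the gap in points, the control-minus-test difference changes by −(mC − mT) × g. For example, 0.64 − (0.06 − 0.03) × 1 = 0.61.

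| mT, mC | g | SD 1.6: difference, power | SD 2.1: difference, power |
|---|---|---|---|
| 5%, 5% | 1 to 3 | 0.64, 0.901 | 0.84, 0.901 |
| 3%, 6% | 1 | 0.61, 0.872 | 0.81, 0.880 |
| 3%, 6% | 3 | 0.55, 0.797 | 0.75, 0.827 |
| 5%, 10% | 1 | 0.59, 0.850 | 0.79, 0.864 |
| 5%, 10% | 3 | 0.49, 0.701 | 0.69, 0.761 |
| 6%, 3% | 1 | 0.67, 0.925 | 0.87, 0.920 |
| 6%, 3% | 3 | 0.73, 0.960 | 0.93, 0.949 |

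Step 3 supports a gap of about 1; the rows with g = 3 are an outer bound.

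A separate simulation used 10 time points, with about 35% v 28% of them after rescue and 10-40% of those missed. Arm means fell by 0.02 to 0.14 points. A difference of 0.60 shrank by 1-3% with equal post-rescue missingness, and became 0.54 or 0.65 when missingness was 30% v 15% in one direction or the other.

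**5. Sensitivity analyses (Section 11.8.1.1)**

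The alternative rescue adjustment again requires an assessed score. The unadjusted analysis removes the rescue adjustment. The observed-case and completer analyses impute nothing. WOCF for all missing scores restores the pre-rescue value only if unscheduled scores count as worst, which is not stated, and it changes every other missing value too.

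**The case against.** The strongest reply is that this is an unstated detail, not a flaw. Section 11.6 defers implementation to a separate SAP, which could impute first and substitute afterwards, or put pre-rescue scores in the imputation model. Either would largely close the gap. A reader might infer that the plan discards the pre-rescue score outright. The documents do not say so, and the same score can still replace another scheduled score recorded within the half-life, as step 2 shows. This much of the reply stands. However, the endpoint rule as written, in three sections, still requires an assessed score.

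A reader might also infer a bias in favour of the test drug, or a large one. The documents support neither. They give no rate of missed entries after rescue, and the sign reverses with the arm that has more of them. The larger effects need an imbalance between arms whose patients are blinded, and no figure in the plan suggests one.

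The plan also limits and exposes missing entries: an 80% compliance threshold in diary practice (Section 5.3.2), completeness review at the Day 2 and Day 3 calls (Section 7.4.3), tabulation of missing data by arm over time (Section 11.6) and the WOCF sensitivity analysis. These reduce or reveal the problem, but none assigns the recorded pre-rescue score to the missed time point.

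**Conclusion.** The point holds as a gap in the derivation of the primary and key secondary endpoints. Followed literally, the rules can treat a missed entry after rescue more favourably than a completed one. Under the assumed inputs, the affected scores are understated by about 1 point on average and arm means by 0.02 to 0.20 points.

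The bias in the treatment difference is likely small. It is zero when the affected shares are equal, 0.03 points at 3% v 6% with a 1-point gap, and of either sign. These sizes rest on assumed missingness, rescue use and correlation, not on figures from the plan. The correction should be made before unblinding because it is nearly free, not because the effect is known to be large.

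**What to change.** In Sections 5.4.2, 8.1, 11.6 and 11.8.1, apply the substitution to every scheduled time within one half-life after rescue, whether the score was assessed or missing, and state the order:

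1. Fill missing scores as now planned: WOCF for dropouts due to adverse event or lack of efficacy, MCMC for the rest.
2. Within each completed dataset, replace the value with the pre-rescue score if the pre-rescue score is higher. For a missed entry, measure the half-life to its scheduled time.
3. State that recorded pre-rescue scores count towards the worst value in WOCF.

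The order matters. Filling the gap with the pre-rescue score before WOCF could lower a dropout's value: with a worst score of 10 and a latest pre-rescue score of 7, it would give 7 where the plan gives 10. It would also drop the plan's if-higher condition and replace multiple imputation with one fixed value. Substituting last keeps the 10, keeps the condition, and retains the imputed value wherever it is the higher.

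The cost is slightly more derivation work and slightly higher adjusted pain scores in both arms. No new data are needed.
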